The research team will consist of the Principal Investigator (PI), Research Assistants (RAs), and Carver College of Medicine Medical Student (MS). 1-4 days prior to scheduled surgery, a member of the research team (and no one outside the research team) will review UIHC Main OR and Ambulatory OR schedules for potential study subjects. On the day of surgery, potential subjects will be seen by a member of the research team and a determination will be made as to their eligibility. If the patient is eligible, the study will be described both verbally by the team member and in writing via the study consent document. After questions are answered, the opportunity to consent will be given. If at any point the patient declines discussion of, or enrollment in, the study, the patient will no longer be eligible for the study and will be removed from the list of potential subjects. To avoid the possibility of coercion or undue influence during the consent process, the study team will make it clear that participation is completely voluntary and that patients will receive the same standard of care whether or not they opt to enroll. If, after discussion, patients are unsure whether they wish to enroll they will be encouraged to decline participation. In addition, if at any point after the time of consent the patient no longer wishes to be involved in the study, they will immediately be excluded from involvement without question.

VII.D.37 *Does the study include any form of deception (e.g., providing participants with false information, misleading information, or withholding information about certain study procedures)?*
Examples:

- *Procedure includes a cover story that provides a plausible but inaccurate account of the purposes of the research.*
- *Participants will be provided with false information regarding the particular behaviors of interest in the research.*
- *Procedures include a confederate pretending to be another participant in the study.*
- *Participants will be told that the research includes completion of a particular task, when in fact, that task will not be administered.*
- *Study is designed to introduce a new procedure (or task) that participants are not initially told about.*
- *If yes, a waiver of informed consent must be requested under question IV.3.*

• No

VII.E. Project Description (E)

VII.E.1 *Will subjects be randomized?*
Yes

VII.E.1.a *Will any subjects be blinded to which study arm they have been assigned?*
No

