- AOA: In the “closed” conformation, insert with concavity facing upward then turn 180 degrees as advancing the proximal bevel to the level of the teeth. Once at the level of the teeth, bring proximal ends together to lock in the fully ‘open’ conformation

12) The CRNA will turn back to the patient and secure the anesthesia mask utilizing “2-handed jaw-thrust” technique.

13) The ventilator is turned on and the following data is recorded, via video of the anesthetic monitor, for breaths # 6-10:

-Inspiratory tidal volumes

-Expiratory tidal volumes

-EtCO₂ waveform

Note (a): If EtCO₂ is not achieved after 5 breaths with first device, proceed immediately to step #14

Note (b): No video or images will be taken of the patient or patient identifiers, just the anesthesia monitor and the device randomized to be placed first

14) The CRNA will then turn away from the patient and the RN research assistant or study medical student will remove the oral airway, noting the presence of any blood on the device (first device only)

15) Steps 10-13 will be repeated for the device randomized to be placed second, then the anesthetic will proceed at the discretion of the providers

Note: If EtCO₂ is not achieved after 5 breaths with the second device, the protocol is ended and the ASA Difficult Airway Algorithm is followed

D. Post-operative:

15-45 minutes after "Anesthesia Stop" time, the research assistant or study medical student will:

- Perform an oropharyngeal exam for signs of trauma

- Ask the patient to grade their degree of “sore throat” (subjectively, from 0-10)

E. Data Review:

-The video taken during step 13 above will be uploaded to a password-protected server to which only study personnel will have access. The video will contain no images of the patient or patient identifiers, just the anesthesia monitor and the device randomized to be placed first

-The blinded primary investigator ([name]) will transcribe clinical data (expiratory and inspiratory tidal volumes and EtCO₂ waveforms) from the above video

VII.E.7

Will you attempt to recontact subjects who are lost to follow-up?

No - followup is not required in this study

VII.E.9

Will subjects be provided any compensation for participating in this study?

No

VIII. Risks

VIII.1

What are the risks to subjects including

- emotional or psychological

- financial

- legal or social

- physical?

- Emotional or psychological: None foreseen

- Financial: None foreseen

- Legal or social: None foreseen

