- Paper/hard copy records (hard copy surveys, questionnaires, case report forms, pictures, etc.) - Paper/hard copy records (hard copy surveys, questionnaires, case report forms, pictures, etc.) - Case report forms will be kept separate from informed consents in 3 hole punched binder. They will be kept in locked file cabinets in a locked office of one of the research assistants. The CRF will have a study ID number for identification. One data list will be kept of the subjects name and ID number for identification purposed on a password protected document within a password protected file. The intraoperative video will contain no images of the patient or patient identifiers, just the anesthesia monitor and the device randomized to be placed first. The video will be uploaded to a password-protected server (backed up and overseen by UI department of anesthesia ITS) to which only study personnel will have access. After upload, the original video will be deleted.
- Electronic records (computer files, electronic databases, etc.) - Electronic records (computer files, electronic databases, etc.) - One data list will be kept of the subjects name and ID number for identification purposed on a password protected document within a password protected file.
 - Name - [name]
 - Title - Information Technology Security Officer
 - University Job Classification - System Administrator and Systems Programmer II

X.5

Do the confidentiality protections indicated above allow only members of the research team to access the data/specimens?

Yes

X.7

Does your study meet the NIH criteria for a [Certificate of Confidentiality](#) or will you be applying for Certificate of Confidentiality?

No

XI. Data Analysis

XI.1

Describe the analysis methods you will use, including, if applicable, the variables you will analyze

We will use non-inferiority testing for the analysis of the primary outcome variable in this study. We will assume that the Articulated Oral Airway is non-inferior to the Guedel oral airway if the difference in expiratory tidal volume measurements between the two devices is less than 1ml/kg.

XI.2

Provide the rationale or power analysis to support the number of subjects proposed to complete this study.

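### The reader of the primary outcome is called blinded, but the video he reads is described as also showing the first-placed device, and no step keeps it from him

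*Combined protocol and SAP*

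**What the plan says.** All references are to the combined protocol and SAP.

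- **What is recorded.** Section VII.E.6 C, step 13, has the volumes and waveforms captured "via video of the anesthetic monitor, for breaths # 6-10". Note (b) to that step adds the first-placed device to the permitted content: "No video or images will be taken of the patient or patient identifiers, just the anesthesia monitor and the device randomized" (the sentence goes on to specify the one placed first). Section VII.E.6 E (Data Review) says the same: "The video will contain no images of the patient or patient identifiers, just the anesthesia monitor and the device randomized to be placed first". Section X.4 repeats it: "just the anesthesia monitor and the device randomized to be placed first".
- **Who reads it.** Data Review names "The blinded primary investigator", who "will transcribe clinical data (expiratory and inspiratory tidal volumes" and CO₂ waveforms) from the video just described.
- **Who may open it.** X.4 places the file on a password-protected server "to which only study personnel will have access. After upload, the original video will be deleted". Section VII.D.29 begins its description of the team: "The research team will consist of the Principal Investigator (PI), Research Assistants (RAs". The reader is therefore among those with access.
- **What is concealed, and from whom.** Section VII.E.6 B keeps the devices out of the clinical providers' view and makes the mask opaque. In VII.E.6 C, step 4 withholds the envelope result from the clinical team, and step 10 has the nurse anesthetist turn away during placement.
- **Design and endpoint.** VII.E.2 sets a crossover in which every patient gets both devices and only the order is random. XI.1 bases the non-inferiority decision on expiratory tidal volume, with a margin of 1 ml/kg.
- **The reader's link to the device.** A note in the attachment list says the primary investigator originally invented the AOA, later assigned the intellectual property to the university, and was found to have no precluding conflict.

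**The concern.** Two consecutive items in Data Review are hard to reconcile. One says the recording shows the device placed first. The other says a blinded reader extracts the data from that recording. With only two devices, knowing the first gives the second, so one image discloses the allocation for both periods.

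The plan recognises the principle: VII.E.2 gives possible bias from a nurse anesthetist who knows the order as a reason to randomize. It protects that person with several steps and states nothing comparable for the reader.

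The single variable behind the non-inferiority conclusion passes through this one transcription, and no second reader is described. The reader's history with the device does not suggest misconduct, but it makes masking that can be demonstrated more valuable. A publication that called the transcription blinded would be claiming something the written procedure does not deliver.

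**Working it through.** **1. The text, side by side**

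| Question | Clinical side | Video reader |
|---|---|---|
| Is the device kept out of view? | Yes: devices out of sight, opaque mask (VII.E.6 B) | No: the recording includes the first device (Note (b), Data Review, X.4) |
| Is the order withheld? | Yes: envelope result not disclosed (step 4) | Not stated |
| Is there a step at the moment of risk? | Yes: the anesthetist turns away (step 10) | Not stated: no editing, separate clip, coded file or viewing order |
| Is access restricted by role? | Not applicable | No: open to study personnel, who include the reader |

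The conclusion about blinding follows from this table and needs no arithmetic.

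**2. Reproducing the plan's power figure**

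Inputs from XI.2: n = 55, SD of the paired difference 2.5 ml/kg, margin 1 ml/kg, one-sided 5% level.

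- Standard error = 2.5/√55 = 0.3371 ml/kg.
- One-sided 5% critical t on 54 degrees of freedom = 1.6736.
- Power at zero true difference = upper tail of the noncentral t with noncentrality 1/0.3371, which is 0.9005. This matches the stated 90%.

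**3. What a reading shift would do (illustration only)**

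Suppose the true difference (AOA minus Guedel) is −1 ml/kg, exactly at the margin, and reading adds an average net shift b toward the AOA. The chance of wrongly declaring non-inferiority is the upper tail beyond 1.6736 of the noncentral t with 54 degrees of freedom and noncentrality b/0.3371.

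| Assumed b (ml/kg) | Equivalent at an assumed 100 kg (ml) | b/0.3371 | False non-inferiority rate |
|---|---|---|---|
| 0 | 0 | 0 | 5.0% |
| 0.02 | 2 | 0.059 | 5.6% |
| 0.05 | 5 | 0.148 | 6.7% |
| 0.1 | 10 | 0.297 | 8.8% |
| 0.2 | 20 | 0.593 | 14.5% |
| 0.3 | 30 | 0.890 | 22.2% |

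Solving for a rate of 10% gives b = 0.124 ml/kg, about 12 ml at 100 kg. Every value of b and the 100 kg weight are assumptions; the documents give neither.

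**The case against.** The strongest reply has four parts.

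- **Timing.** During breaths 6-10 the device is in the mouth under an opaque mask, and images of the patient are barred. Any device image must therefore come before insertion or after removal. If it was taken at removal, period 1 could be read before the device appears. This stands as far as it goes. However, the plan does not say when the device is filmed, describes one video containing both, and sends the reader to that video. Period 2 would be exposed in a single file even under the favourable order.
- **Purpose of the repeated sentence.** The three statements read as a privacy limit on filming, and step 13 mentions only the monitor. It is fair to count them as one sentence reused rather than three confirmations. Data Review nevertheless makes that recording the reader's source.
- **Unseen attachments.** The list includes a blinded video review form, a full study protocol, and a checklist and role sheet for the research assistant. Any of these might contain a masking step. That possibility stays open, so the finding concerns the text available. It does not show that unblinding happened.
- **Objectivity.** Displayed numbers on prespecified breaths leave little room for judgement, an average misreading of 10-30 ml in one direction would need a mechanism, and the stored video permits re-checking. This carries real weight on size. It does not make the blinding claim true as written, and no re-reading is planned. The waveforms, part of the first research question in I.5, may leave more room for judgement.

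**Conclusion.** The concern holds. Followed as written, the plan gives a reader it calls blinded a recording that discloses the device order, and it states no safeguard for him. This should be fixed, but it does not threaten the design: sample size, power and margin are unaffected, and the main route for bias, the person delivering ventilation, has stated concealment.

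The size of any bias is unknown and may be near zero. The error rates above show only how sensitive the test would be to assumed shifts; the conclusion does not depend on them. It does depend on no masking step existing in the attachments that were not available, and on the device footage not being withheld from the reader in some way the text leaves out.

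**What to change.** - Keep the device out of the video the reader receives. Supply two monitor-only clips per patient, labelled period 1 and period 2.
- Hold the device image in a separate file that the reader cannot open, or record the first device on the research assistant's form. The separate file is safer if the image is wanted for documentation, because a form entry alone would lose it, and the form's content could not be checked here.
- Release the device order only after the transcription is locked.
- Amend Note (b), Data Review and X.4 to match, and restrict server access by role.
- If an attachment already contains a masking step, state it in Data Review and set the access rule accordingly.

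The cost is minor file handling (two clips per patient and one restricted file) and wording in three places. The research assistant already opens the envelope, knows the order and has a data form, so no extra staff are needed. Patient procedures, sample size and analysis do not change.

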- The anesthesia ventilator will be pre-programmed to Pressure Control mode at 15cm H₂O with a rate of 10 breaths/minute and an inspiratory:expiratory ratio of 1:3
- A video recording device will be available to record data from the anesthetic monitor

C. Induction/Airway Management. On arrival to the operating room:

- 1) Apply standard ASA monitors
- 2) Apply Entropy monitor (measures depth of anesthesia via evaluation of brain EEG and quantitative Train of Four (TOF, routine intraoperative monitor which measures level of paralysis via evaluation of the response to electrical stimulus)monitors
- 3) Pre-oxygenate until end tidal O₂ is >90% or for >3 minutes
- 4) Research assistant will open the randomization envelope but not disclose the randomized device order to the clinical team
- 5) IV Induction: 1-2mg midazolam, 50-100mcg fentanyl, 60-100mg lidocaine and 1-2mg/kg propofol.
- 6) Maintenance of anesthesia: 100mcg/kg/min propofol started at time of induction.
- 7) Once lid reflex is lost, obtain a baseline quantitative train-of-four (TOF) and administer rocuronium 1mg/kg of real body weight
- 8) One-handed mask ventilation (MV), without an oral airway, is initiated by the Certified Nurse Anesthetist (CRNA). If one-handed MV without an oral airway is insufficient to return any EtCO₂, a “two-handed jaw-thrust” technique, without an oral airway, is utilized until paralysis/anesthetic depth measures are met. If two-handed technique is insufficient, the 28Fr nasopharyngeal airway is placed and two-handed technique restarted. If two-handed MV with a 28Fr nasopharyngeal airway does not return any EtCO₂, proceed to step #10.
- 9) Once the quantitative TOF is <20% and Entropy reading is 40-60[3], proceed to step 10
 - If, after 90 seconds, the TOF is not <20%, continue to MV until the TOF is <20%
 - If, after 90 seconds, the Entropy reading is not 40-60, increase propofol by 50mcg/kg/min every minute and continue MV until reading is 40-60
- 10) The CRNA (who is performing MV) is asked to turn away so as to be blinded to oral airway placement order
- 11) The RN research assistant or study medical student (both formally trained, with documentation, in oral airway placement) will place the device randomized to be first using the below methods and then cover the patients nose and mouth with the opacified anesthesia mask
 - Guedel oral airway: Insert with concavity facing upward then turn 180 degrees as advancing the proximal bevel to the level of the teeth

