- Physical: Potential for risks associated with routine airway management with an oral airway (difficult or failed airway management/oropharyngeal trauma). Potential for risks associated with placement of two oral airways instead of just one or none.

VIII.2

What have you done to minimize the risks?

- *If applicable to this study ALSO include:*
 - *How you (members of your research team at Iowa) will monitor the safety of individual subjects.*
 - *Include a description of the availability of medical or psychological resources that subjects might require as a consequence of participating in this research and how referral will occur if necessary (e.g. availability of emergency medical care, psychological counseling, etc.)*

Pre-procedure: The Articulated Oral Airway is made of bio-compatible material in a ISO 9001:2008 Certified molding facility. The AOA has been tested in manakin models, including pressure testing by members of the UIowa Biomedical Engineering program.

Intraoperative: Per protocol, if difficulty in airway management is encountered, the study is abandoned and emergency airway management protocols (ASA Difficult Airway Algorithm) followed.

Post-operative: An interim safety review will be performed after 20 patients have been enrolled. If there is any significant increase in either trauma or difficult in mask ventilation noted, the study will be stopped.

VIII.3 *Does this study have a plan to have an individual or committee review combined data from all subjects on a periodic basis (such as summary or aggregate safety and/or efficacy data)?*

Yes

VIII.4 *Describe the plan to review combined data from all subjects, such as summary or aggregate safety and/or efficacy data. Include the following:*

- *Describe what data will be summarized and reviewed*
- *Describe how frequently data will be reviewed.*

After the first 20 patients (and any time earlier if concerns are raised by the research team/clinical staff caring for the patients), a unbiased faculty anesthesiologist ([name], as per below) will review intraoperative tidal volumes (marker for adequate ventilation), incidence of blood on first-placed device, and post-anesthesia care unit (PACU) data on post-operative pharyngeal trauma.

VIII.5 *Will overall safety monitoring be performed by individual(s)/committee at The University of Iowa. (NOTE: If this study involves more than minimal risk, in most cases these should be individuals who are not members of the study research team.)?*

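### A device that returns no EtCO2 leaves no tidal volume for the paired non-inferiority test, and the plan gives no rule for analysing or counting that failure

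*Combined protocol and SAP*

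**What the plan says.** - **What is measured.** In VII.E.6 C, step 13, once the ventilator is on, "the following data is recorded, via video of the anesthetic monitor, for breaths # 6-10". The items are inspiratory and expiratory tidal volumes and the EtCO2 waveform.
- **First device fails.** Step 13 Note (a): if EtCO2 "is not achieved after 5 breaths with first device, proceed immediately to step #14". Step 14 is removal of the device, and step 15 goes on to the second device.
- **Second device fails.** Step 15 Note: if EtCO2 "is not achieved after 5 breaths with the second device, the protocol is ended and the ASA Difficult Airway Algorithm is followed".
- **Airway difficulty in general.** VIII.2 (intraoperative): "Per protocol, if difficulty in airway management is encountered, the study is abandoned", and the ASA algorithm is followed.
- **Primary analysis.** XI.1 and XI.2 compare expiratory tidal volume between devices with a paired t-test, margin 1 ml/kg and one-sided 0.05. The target is 55 pairs; 58 patients are recruited to allow for 3 protocol failures, a term that is not defined. Neither section says what happens to a patient with no volume on one device.
- **Safety review.** VIII.2 (post-operative): "If there is any significant increase in either trauma or difficult in mask ventilation noted, the study will be stopped". VIII.4 says that after 20 patients a faculty anesthesiologist "will review intraoperative tidal volumes (marker for adequate ventilation), incidence of blood on first-placed device", and recovery-room data on pharyngeal trauma. Review may come earlier: "any time earlier if concerns are raised by the research team" or by the clinical staff.

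**The concern.** The study asks whether the AOA ventilates as well as the Guedel in patients chosen because they have at least two risk factors for difficult mask ventilation. A device that returns no EtCO2 at all gives the clearest possible answer for that patient. Under step 13 and the two Notes, it is also the one result that produces no primary data. Patients lost in this way are lost because of the outcome, so the remaining pairs describe only patients in whom both devices worked.

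In a non-inferiority comparison such a loss can hide a real disadvantage of the new device, or of the comparator. The event is foreseeable, since the procedure has explicit rules for it, but the analysis section has none. The ventilation item listed for the 20-patient review rests on the same breath 6-10 volumes, although difficulty in mask ventilation is a stated reason to stop.

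**Working it through.** **1. The plan's own figure.** Inputs from XI.2: margin 1 ml/kg, SD of the paired difference 2.5 ml/kg, one-sided 0.05. The true difference is taken as 0. Power is P(T > t(0.95, n-1)), where T is noncentral t with n-1 degrees of freedom and noncentrality (1/2.5)√n. At n = 55 this is 0.9005, and 55 is the smallest n that reaches 0.90. Then 55 + 3 = 58. The sample size is correct and is not at issue.

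**2. Where the value goes missing.**

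| Event | Breath 6-10 volume, first device | Breath 6-10 volume, second device | Pair usable? |
|---|---|---|---|
| Both devices work | yes | yes | yes |
| First fails, second works | no | yes | no |
| First works, second fails | yes | no | no |
| Both fail | no | no | no |

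**3. Lost pairs and power.** Three lost pairs are already allowed for. Beyond that, power is 0.8956 at 54 pairs, 0.8905 at 53 and 0.8851 at 52. The effect is negligible; the problem is selection, not precision.

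**4. Size of the selection effect.** The documents give neither a failure rate nor a working tidal volume, so this step is illustrative. Assume that the failed device scores 0 ml/kg and the other device gives V ml/kg in the same patient. The mean difference over n patients then shifts by kV/n for k failures of one device. With k = 3 and n = 58:

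- V = 2: 3 × 2 / 58 = 0.10 ml/kg
- V = 4: 3 × 4 / 58 = 0.21 ml/kg
- V = 8: 3 × 8 / 58 = 0.41 ml/kg

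The margin is 1 ml/kg.

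**5. Chance of showing non-inferiority.** This was simulated with 58 - k pairs drawn from a normal distribution (mean 0, SD 2.5), plus k pairs fixed at -V (AOA fails) or +V (Guedel fails), and the XI.2 test applied to all 58.

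| Failures | Pairs dropped | AOA fails, V = 2 / 4 / 8 | Guedel fails, V = 2 / 4 / 8 |
|---|---|---|---|
| 1 | 91% | 90 / 88 / 80% | 93 / 94 / 95% |
| 3 | 90% | 87 / 76 / 40% | 96 / 97 / 99% |

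The fall on the AOA side has two sources: the mean shifts, and the extreme values widen the SD.

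**6. How likely failures are.** At assumed per-patient failure rates of 2%, 5% and 10%, the binomial chance of at least one failure in the first 20 patients is 33%, 64% and 88%. The chance of more than 3 in 58 is 3%, 33% and 84%.

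**The case against.** **The plan never says that such pairs are dropped.** This is true: the text is silent, and silence would also permit scoring the failed device as 0. But a paired t-test on recorded volumes has nothing to enter for that device unless a rule supplies it. Omission is the default in practice, not a stated intention.

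**The safety reviewer would see the failures.** A reader might infer from the VIII.4 list that failures are invisible at the 20-patient review. The documents do not support that. The reviewer looks at tidal volumes, not at a complete-pair mean, and a blank among 20 patients would show. Staff witness each failure and can trigger an earlier review. What stands is narrower: no count of failures is listed, although mask-ventilation difficulty is a stopping reason.

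**VIII.2 contradicts the steps.** A reader might infer this too, because step 8 sends a patient on to the devices when "If two-handed MV with a 28Fr nasopharyngeal airway does not return any" EtCO2, and Note (a) goes on to the second device. But VIII.2 reads naturally as a summary of the step 15 Note, which invokes the same algorithm, or as a general override. Going on to an airway aid not yet tried is ordinary escalation. At most this is a matter of wording.

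**Failures may be rare, and the figures rest on assumptions.** The exclusions, deep paralysis and two-handed jaw thrust may make absent EtCO2 uncommon. A patient in whom one device fails may also ventilate poorly on the other; at V = 2 the effect of 3 failures is small. The 40% figure needs three failures, all on the AOA, with 8 ml/kg on the Guedel each time. This limits the size, not the gap.

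**The waveform is also a stated measure.** Research question 1 names it, but step 13 records it for the same breaths, and XI gives no analysis of it.

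**The forms may already capture failures.** The attachment list includes a full protocol and data collection forms that were not available for this review. They might record the event; XI and VIII.4 would still not use it.

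**Conclusion.** The concern holds in a limited form and should be addressed. Followed as written, the primary test has no value for a device that returns no EtCO2 after 5 breaths and would in practice leave out the patients with the worst ventilation results. XI.1 and XI.2 give no rule, and it is unclear whether these patients are among the 3 protocol failures.

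The size is unknown. With three AOA failures the chance of showing non-inferiority is 90% if the pairs are dropped and 87% to 40% if they are scored 0, for an assumed Guedel volume of 2 to 8 ml/kg. These figures assume no true difference in the other pairs and the plan's SD. If the Guedel is the device that fails, scoring raises the chance to 96-99%. A reader might infer that the gap favours the AOA; the documents do not show that, because they give no failure rate for either device.

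**What to change.** 1. Record each no-EtCO2 failure, with the device and whether it was placed first or second, unless the forms already do so.
2. Report these counts by device and order beside the primary non-inferiority result.
3. In XI.1, keep the paired test as primary and state how patients without a volume are handled in it. Add a sensitivity analysis that scores a failed device as 0 ml/kg. List separately any patient in whom both devices fail or the second is never tried: scoring both as 0 would give a difference of 0 and would wrongly count as evidence of similarity.
4. In XI.2, say whether these patients count toward the 3 protocol failures.
5. Add the failure counts by device to the items reviewed after 20 patients in VIII.4.

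Zero-scoring is one reasonable choice among several; what matters is that the rule is fixed before the data are seen. The cost is one data field, one extra analysis and a short amendment. The sensitivity analysis may make the non-inferiority conclusion less favourable. The primary test, the sample size and the procedures do not change.
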